	Study Number:	IF# 1896970; GCO# 16-0945

severe exacerbations, and increased risk of intubation.⁵⁵⁻⁵⁸ Key cytokines driving neutrophilic asthma include IL-1 β , IL-6 and IL-17, which are elevated in patients with PTSD.⁵¹ IL-6 directs and stabilized T-cells towards a Th17 subset,⁵⁹⁻⁶² which can then recruit and activate of neutrophils.⁶³⁻⁶⁶ Therefore, systemic inflammatory changes associated with PTSD, may worsen asthma outcomes by driving a neutrophilic asthma phenotype. Identification of the biological pathways underlying worse asthma in patients with comorbid PTSD has important implications for disease management including indications for inhaled corticosteroids (ICS) and new biological drugs and may offer new alternative targets for therapy.^{67,68}

Symptom Perception in Asthma Patients with Comorbid PTSD: Effective asthma SMB requires the patient to recognize and respond (use of rescue medication, contact physician, etc.) to their symptoms.^{69,70} Self-monitoring of symptoms is also key for assessing response to treatment and thus, developing effective self-regulatory mechanisms (i.e., ICS linked to improved symptoms; see theoretical framework). Unfortunately, the symptoms that asthma patients experience do not always align with objective measures of their airway obstruction.⁷¹⁻⁸¹ Experiments have identified 3 asthma symptom perception phenotypes that have important clinical implications: symptom under-perceivers, normal perceivers, and over-perceivers.^{78,82-84} Prior studies have shown a strong relationship between misperception of symptoms and increased asthma morbidity.^{77,85-88}

While PTSD is associated with increased objective and subjective asthma morbidity markers, the associations with subjective measures are stronger.^{16,18} We found that PTSD had strong associations with disease control measures and quality of life in WTC workers with asthma.¹⁷ However, the association with FEV₁ was weaker (see preliminary data). Other studies had similar findings.¹⁶⁻²⁰ These data strongly suggest that over-perception of symptoms may be prevalent among WTC workers with PTSD and may contribute to increased asthma morbidity and complicate SMB.

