Asthma Symptom Perception: We will use the AM2 computerized peak flow monitor (ERT Corporation, Philadelphia, PA; Figure 2) to assess symptom perception by comparing actual and perceived PEF values for 4 weeks following the baseline, 6- and 12-months interviews.^{77,109,184} Following a well validated protocol, RAs will train participants to enter the PEF estimate (step 1) and then perform the PEF effort (step 2). To help them estimate their PEF, the RA will attach a colored sticker to the AM2 showing the participant's predicted PEF values (based on age, sex and height) that correspond to the go (green), caution (yellow), and danger (red) zones of asthma control (Figure 3).¹⁷² After entering their estimated PEF, participants will perform 3 maximal effort blows, with 2 minute rests between each. The actual peak flow values of each blow will not appear on the device. The AM2's acoustic alarm will remind them to use it in the morning and evening.

	Protocol Title:	Assessing Inflammatory and Behavioral Pathways Linking PTSD to Increased Asthma Morbidity in WTC Workers
	Principal Investigator Name/Contact Info:	[name], DrPH [contact]; [contact]
	Primary Contact Name/Contact Info	[name], MS [contact]; [contact]
	Date Revised:	07/25/16
	Study Number:	IF# 1896970; GCO# 16-0945

The asthma risk grid (Figure 4) was developed to quantify symptom perception accuracy.^{77,109,172,184,185} Each objective PEF is plotted against the corresponding subjective estimate of PEF to generate a percent of objective personal best. Patients' estimates are categorized in the *accurate*, *under-perception*, and *over-perception* zones, and must be at least 10% higher or lower than the actual PEF value (to ensure that estimates close to the accurate zone are not classified as inaccurate) to be considered in these zones, respectively. Each participant's symptom perception will be characterized as the percent of time they spend within each perception zone. The percentage of estimates in the over-perception one will be the main study measure. Home Peak Flow Meter (PFM) use: We will ask patients with their own PFM's not to use them while they are using the AM2. In our prior studies, <5% of participants used a PFM ≥ 1 time/week.

Figure 2: AM2 Peak Flow Meter

Figure 3. AM2 Sticker to Help Patients Estimate their PEF

[figure not shown]
[figure not shown]

Figure 4. Asthma Risk Grid

C. Asthma SMB: will be based on NIH guidelines.¹⁷² Asthma Controller Medication Adherence:

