Sputum Neutrophilia	0.25	0.30	106
Sputum Eosinophilia	0.50	0.25	107
IL-6, pg/ml	4 (2)	2	67

 Mount Sinai	Protocol Title:	Assessing Inflammatory and Behavioral Pathways Linking PTSD to Increased Asthma Morbidity in WTC Workers
	Principal Investigator Name/Contact Info:	[name], DrPH [contact]; [contact]
	Primary Contact Name/Contact Info	[name], MS [contact]; [contact]
	Date Revised:	07/25/16
	Study Number:	IF# 1896970; GCO# 16-0945

Power Calculations: Assumptions about the expected retention rate ($\geq 80\%$), the prevalence of PTSD ($\sim 30\%$) and the distribution of inflammatory markers were derived from our preliminary data and the literature.^{1,7,8} Under these assumptions, with 175 participants undergoing sputum induction, the study will be powered to test Aim 1 hypotheses (Table 3).

Aim 2. Examine the longitudinal association between PTSD and symptom perception in WTC workers with asthma: We will calculate the proportion of blows that each participant over-estimate using AM2 data. A probit transformation will be applied to normalize the proportion of over-perceived guesses; differences in the distribution of the transformed variable at each time point in participants with and without PTSD will be assessed with a t-test.²²⁷ We will use a GEE model to assess the association between PTSD and symptom perception over time.²²⁸ We will then fit a fixed effects model (i.e., limited to within subject variability) to assess the longitudinal effect of changes in PTSD symptoms (PCL scores) on symptom perception. We will repeat these analyses adjusting for potential confounders as described above.

[figure not shown]
We will also assess the correlation between subjective (ACQ scores, use of beta2-agonists, AQLQ scores) and objective (FEV₁) measures of morbidity separately in asthmatics with and without PTSD and apply a Fisher's z' transformation to assess if the association varies between these groups. Then, we will fit a GEE model with ACQ scores (or use of beta2-agonists/AQLQ) as the dependent variable and as predictors, FEV₁, PTSD status, and an interaction between PTSD and FEV₁. In this model, the interaction term will test whether the association between objective and subjective measures varies according to the participant's PTSD status.

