Power Calculations: We estimated rates of over-perception and asthma morbidity from our prior studies or the literature.^{27,109,154,155,168,229} We adjusted the sample size for the expected correlation of measurements within a participant (interclass correlation coefficient ≥ 0.8).²³⁰ These analyses showed that with 400 patients, the study will have $>90\%$ power to detect a 10% increase in the probability of over-perception in participants with PTSD. We also evaluated the power to identify whether the regression coefficients for the association between the ACQ/AQLQ scores and FEV₁ is different for patients with vs. without PTSD (equivalent to testing an interaction). These analyses showed that with 400 subjects (and 80% retention), the study will have an 82% power to detect a difference of 1 unit between the slopes of patients with and without PTSD.

Aim 3. Assess the relationship between PTSD and adherence to asthma SMB in WTC workers and identify the pathways linking them: Medication adherence analyses will be restricted to patients prescribed controller medications ($>80\%$ of the sample based on prior studies). Primary analyses will use electronic adherence measures; secondary analyses will use MARS scores and other SMB. The univariate association of adherence and PTSD will be assessed using a chi-square test. Multivariable analyses will use a GEE model (logit link function) to control for potential confounders as listed above. We will use similar approaches to assess the associations of potential mediators (over-perception of symptoms, anxiety sensitivity, and illness and medication beliefs, Figure 5) of the relationship between PTSD and medication adherence.

 Mount Sinai	Protocol Title:	Assessing Inflammatory and Behavioral Pathways Linking PTSD to Increased Asthma Morbidity in WTC Workers
	Principal Investigator Name/Contact Info:	[name], DrPH [contact]; [contact]
	Primary Contact Name/Contact Info	[name], MS [contact]; [contact]
	Date Revised:	07/25/16
	Study Number:	IF# 1896970; GCO# 16-0945

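### The main Aim 2 measure, the share of guesses in the over-perception zone, does not separate a directional shift in perception from imprecise guessing, and no planned Aim 2 analysis of the guesses does so

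*Combined protocol and SAP*

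**What the plan says.** Under Asthma Symptom Perception in section f), participants enter a guess of their PEF and then blow into the AM2, with the result hidden. The device's alarm is to "remind them to use it in the morning and evening", and it is used "for 4 weeks following the baseline, 6- and 12-months interviews". Each guess is placed on an asthma risk grid (Figure 4, not shown in the text available) as accurate, under-perception or over-perception. To count in either inaccurate zone, a guess "must be at least 10% higher or lower than the actual PEF value". Over-perception is the low side: the participant believes airflow is worse than it is.

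All three zones are recorded: "Each participant's symptom perception will be characterized as the percent of time they spend within each perception zone". Only one is carried forward: "The percentage of estimates in the over-perception one will be the main study measure".

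The Aim 2 paragraph of the Data Analyses uses that share throughout: "A probit transformation will be applied to normalize the proportion of over-perceived guesses". A t-test compares PTSD groups at each time point, a GEE model covers all time points, and a fixed effects model relates within-person change in PCL score to perception. Adjustment refers back to the Aim 1 confounders. Those named are age, sex, race/ethnicity, adherence-adjusted ICS dose, asthma onset relative to WTC exposure, BMI, comorbidities and depression. The list is open-ended, but names no PEF level, PEF variability or FEV₁. No Aim 2 analysis uses the under-perception share or the signed difference between guess and PEF.

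The Aim 2 power statement claims more than 90% power with 400 patients for "a 10% increase in the probability of over-perception in participants with PTSD".

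**The concern.** H2a is a directional claim: participants with PTSD judge their airflow to be worse than it is. The share tested is a tail probability of the guessing error, so it depends on both the centre and the spread of that error. A group that guesses less precisely, but is right on average, has more guesses in both tails and therefore a higher over-perception share. The under-perception share or the mean error would show the difference at once, but neither is examined by PTSD status.

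Three things rest on this contrast: H2a, the use of over-perception as a mediator in H3b, and the Aim 4 decision to build perception training into the pilot if Aim 2 shows over-perception in participants with PTSD. If the finding were really imprecision, all three would rest on a misreading that the plan has no check to reveal.

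**Working it through.** **1. The plan's power figure.** No baseline rate, SD, alpha or sidedness is given for Aim 2, so the figure can be matched but not checked. Inputs: N = 400; PTSD prevalence about 30% (Aim 1 power text), giving 120 and 280; within-participant correlation 0.8; 3 windows. Assumed: SD of the share 0.30, two-sided alpha 0.05.

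- Repeated-measures factor: (1 + 2 × 0.8)/3 = 0.867.
- SE = 0.30 × √0.867 × √(1/120 + 1/280) = 0.0305.
- Power = Φ(0.10/0.0305 − 1.96) ≈ 90.7%.

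An SD of 0.25 gives 97.6% and 0.35 gives 80.3%. The stated power is attainable and is not shown to be wrong.

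**2. Why the share mixes two things.** Take the 10% margin alone as the rule. Let the relative guessing error (guess minus actual, over actual) be normal with mean b and SD s. Then

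- over share = Φ((−0.10 − b)/s)
- under share = 1 − Φ((0.10 − b)/s)

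| Case (assumed values) | Over | Under |
|---|---|---|
| b = 0, s = 8% | Φ(−1.25) = 10.6% | 10.6% |
| b = 0, s = 12% | Φ(−0.833) = 20.2% | 20.2% |
| b = −3.33%, s = 8% | Φ(−0.833) = 20.2% | 1 − Φ(1.667) = 4.8% |

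Rows 2 and 3 have the same over-perception share. One is pure imprecision and the other a real shift. Only the under share (20.2% against 4.8%) or the mean error (0 against −3.33%) tells them apart. The gap between rows 1 and 2 is 20.2 − 10.6 = 9.6 points.

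The grid may also require a mismatch of colour zone. With assumed zone cut-points at 50% and 80% of personal best and mean PEF at 85%, the same change in noise moves the over share from 6.3% to 13.2%, so this route does not depend on the 10% margin being the whole rule.

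**3. What the planned test would do.** Simulation: 280 against 120 participants; 2 × 28 = 56 readings in one window; probit-transformed share; two-sided t-test at 0.05. Assumed: mean PEF 85% of best, PEF SD 8 points, guesses following PEF halfway, no group difference in bias. The table gives the percentage of replicates significant in the H2a direction (nominal 2.5%), by between-person SD of bias.

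| PTSD group differs by | Bias SD 3 | Bias SD 6 | Bias SD 10 |
|---|---|---|---|
| nothing, 10% rule | 2.3 | 2.5 | 1.8 |
| guess SD 10 instead of 8 points, 10% rule | 99 | 61 | 20 |
| same, 50/80 zone rule | 99 | 76 | 33 |
| same, tested on mean signed error | 3.0 | 2.5 | 2.3 |
| guess SD 12 instead of 8 points, 10% rule | 100 | 99 | 59 |

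At bias SD 6, going from guess SD 8 to 10 raises over-perception from 20.9% to 24.1% and under-perception from 22.2% to 25.1%. For a true downward bias of 3 points, power is 76–100% with the planned share under the 10% rule and 78–100% with mean signed error, so little is lost by looking at direction.

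**4. PEF variability and level.** Same set-up, guess SD 8, with PEF SD 12 instead of 8 in the PTSD group:

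- Guesses do not follow PEF: 99%, 69%, 24% under the 10% rule; 3–7% under the zone rule.
- Guesses follow halfway: 35%, 14%, 6%; about 0% under the zone rule.
- Guesses follow fully: 2.5–3.2%; about 0% under the zone rule.

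With mean PEF 80 instead of 85 and guesses following fully, the rates are 26%, 12% and 7% under the 10% rule and about 0–1% under the zone rule. If guesses follow halfway and lag toward the higher level, over-perception falls (21.0% to 15.9% at bias SD 6), under-perception rises (22.2% to 31.0%), and the false H2a rate is 0.

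**The case against.** A reader might infer that worse asthma by itself can produce a positive H2a, since the Background says: "While PTSD is associated with increased objective and subjective asthma morbidity markers, the associations with subjective measures are stronger". The documents do not support that reading. The same section describes the FEV₁ association as weaker and reports nothing on PEF lability. Step 4 shows that variability matters only when guesses fail to follow PEF, and mainly if the 10% margin is the whole rule. The text reads more naturally as a buffer added to grid zones whose boundaries cannot be seen here. Lower PEF with lagging guesses works against H2a. This part of the objection stands in full.

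It can also be said that no document gives guessing error by PTSD status, so every SD above is assumed. That stands too: the calculations show that the problem can occur, not how large it is.

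The plan has partial safeguards. The fixed effects model largely removes stable differences between people in guessing precision, but it tests change in PCL score, not the between-group contrast in H2a. The confounder list is open and includes ICS dose, but adjusting for severity does not remove guessing error. H2b relates subjective measures to FEV₁ and is a separate question.

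Finally, the AM2 protocol is described as well validated, and frequency of over-perception is a legitimate quantity. Mean signed error is a different one: a person who over-perceives on some days and under-perceives on others can average zero. That is a good reason not to replace the main measure. It is no reason to leave direction unexamined.

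**Conclusion.** The concern holds in limited form. The over-perception share cannot distinguish a directional shift from less precise guessing, and the planned t-test and GEE can support H2a on imprecision alone. This holds under both readings of the zone rule tried. In the assumed scenarios, a guess SD of 10 rather than 8 points gives a false H2a finding in 20–99% of studies under the 10% rule and 33–99% under a 50/80 zone rule, against a nominal 2.5%. These figures rest on assumed PEF level, tracking, error SDs and between-person bias. The actual bias is unknown and may be small.

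PEF variability is a secondary and conditional route, depending on tracking, mean PEF and the grid boundaries. The power statement is not shown to be wrong. This is a cheap improvement to the analysis plan, not a reason to abandon the measure.

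**What to change.** Keep the over-perception share as the main measure, and add the following to the Aim 2 analysis text:

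- **Required companion.** Mean signed error (guess minus actual PEF, as a percentage of personal best) per participant and window, compared by PTSD status in the same GEE. Do not include participant fixed effects in this model, since they would absorb the between-person PTSD contrast. The over-minus-under share is an alternative. It performed nearly as well under the 10% rule (0.7–5.5% false findings), but if the grid also needs a zone change the two tails need not be symmetric, so signed error is safer.
- **Both tails.** Report the under-perception share beside the over-perception share, by PTSD status and window.
- **Sensitivity adjustment.** Add mean PEF and PEF coefficient of variation from the same AM2 window.
- **Conclusion rule.** Conclude over-perception for H2a, for the H3b mediator and for the Aim 4 pilot decision only if the shift is directional. If both tails rise together, report imprecise perception.

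All quantities come from AM2 data already planned, so the cost is wording and a little more analysis. The condition for claiming H2a becomes stricter. Signed error can average out in people who misjudge in both directions, which is why both zone shares are shown with it.

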generalized linear model to assess the association of PTSD with sputum eosinophilia or neutrophilia (logit link), or cytokine levels (identity link) after controlling for possible confounders such as age, sex, race/ethnicity, ICS dose (calculated after adjusting for adherence), asthma onset in relation to WTC exposure, BMI, comorbidities, and depression. We will calculate the false discovery rate from the p-values to control for testing of multiple cytokines.²²³ Then, we will assess the unadjusted association of plasma and sputum cytokine levels as well as the associations of airway eosinophilia, neutrophilia, and cytokines levels with measures of asthma control using correlation coefficients or Wilcoxon test. The adjusted relationship of inflammatory markers (systemic and sputum) and asthma control measures over time will be assessed using generalized estimating equation (GEE) models (logit or identity link and autoregressive correlation structure for repeated measures over time). The model will include an interaction between inflammation markers (e.g., neutrophilia, etc.) and PTSD status to assess for potential effect modification (i.e., differential effect in subjects with vs. without PTSD). Finally, we will fit a fixed effects model (i.e. limited to within subject variability) to assess the longitudinal effect of changes in systemic cytokines levels on asthma morbidity makers.

We will use structural equation modeling (SEM; see details below) to test whether systemic inflammation, leading to airway neutrophilia and high IL-6 levels, mediates the association between PTSD and increased asthma morbidity. Following the MacArthur approach²²⁴ for assessing mediation, main effects as well as interactions between PTSD and inflammatory markers will be included as predictors of asthma morbidity.^{225,226} The analyses described above will establish if PTSD has a significant effect on the mediators (i.e., inflammatory markers), which is the first step of mediation. What is then needed is to also show that these factors are also associated with asthma morbidity measures while controlling for PTSD. Building a SEM including inflammatory markers, PTSD and an interaction variable of PTSD with the potential mediators, while controlling for other confounders, will provide a formal test of mediation.

Table 3. Power Calculations for Aim 1

Outcome	Proportion/ Mean among Participants without PTSD	Δ Proportion/ Mean for Participants with PTSD	Sample Size for 80% Power

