Next, an overall unconditional model will be fitted to identify the growth trajectory across time. To that end, we will fit a growth function for anxiety sensitivity, symptom perception, illness beliefs, and asthma SMB using linear, quadratic, and unstructured models. Relative model fit will be evaluated based on the: χ^2 index ($>.05$), the comparative fit index ($>.97$), the root mean squared error of approximation (RMSEA $<.05$), and the weighted root mean square residual when using WLSMV (WRMR $<.90$). The most parsimonious model with the best fit will be retained. Finally, we will fit the full structural model, including the hypothesized relationships. For example, PTSD will be included as a predictor of asthma SMB. To address the possible mediational effects of anxiety sensitivity, symptom perception, illness and medication beliefs on the relationship between PTSD and asthma SMB, we will fit models to estimate both direct and indirect effects, first separately, and then combined. Lagged effects of the time-varying predictors, as well as the effects of the latent growth variables themselves (intercept, slope, and their random effects) will be evaluated as potential mediators; we will also be able to assess models of complete vs. partial mediation.¹²⁸ Relative fit, as well as estimates of effect size will be calculated, along with Sobel tests and Monte Carlo CIs to evaluate the mediational hypotheses.²³⁴

 Mount Sinai	Protocol Title:	Assessing Inflammatory and Behavioral Pathways Linking PTSD to Increased Asthma Morbidity in WTC Workers
	Principal Investigator Name/Contact Info:	[name], DrPH [contact]; [contact]
	Primary Contact Name/Contact Info	[name], MS [contact]; [contact]
	Date Revised:	07/25/16
	Study Number:	IF# 1896970; GCO# 16-0945

Integrating Biological and Behavioral Pathways: Finally, we will employ LGCM to characterize the interrelation and relative contribution of biological and behavioral pathways linking PTSD and asthma morbidity (Figure 1).

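### The Aim 1 mediation criteria specify no PTSD-adjusted path from systemic to airway inflammation, so they cannot tell the claimed chain from parallel, unlinked mediators

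*Combined protocol and SAP*

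**What the plan says.** In section h), Data Analyses, Aim 1, the purpose of the SEM is "to test whether systemic inflammation, leading to airway neutrophilia and high IL-6 levels, mediates the association between PTSD and increased asthma morbidity". The words 'leading to' place the airway markers downstream of the systemic ones.

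The same paragraph then gives the criteria:

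- **Step 1.** The preceding regressions will "establish if PTSD has a significant effect on the mediators (i.e., inflammatory markers), which is the first step of mediation".
- **Step 2.** "What is then needed is to also show that these factors are also associated with asthma morbidity measures while controlling for PTSD".
- **Formal test.** "Building a SEM including inflammatory markers, PTSD and an interaction variable of PTSD with the potential mediators", with control for other confounders, is described as the formal test of mediation.

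Outside the mediation test, and earlier in the Aim 1 text, "we will assess the unadjusted association of plasma and sputum cytokine levels". It covers cytokines, not neutrophilia.

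The Aim 1 paragraph refers to SEM details further down. Those are in the Aim 3 text on latent growth curve modeling: "we will fit models to estimate both direct and indirect effects, first separately, and then combined", "along with Sobel tests and Monte Carlo CIs to evaluate the mediational hypotheses". They are written for the behavioral mediators, and name no systemic-to-airway path.

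**The concern.** The chain has three links: PTSD to systemic, systemic to airway, and airway to morbidity. It fails if any one is zero. Step 1 covers PTSD to each marker, and step 2 covers marker to morbidity. The middle link is in neither. If PTSD raises plasma and sputum markers by separate routes, step 1 still passes, and step 2 passes whenever the markers predict morbidity.

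The planned plasma-sputum association does not close the gap. H1a expects PTSD to raise systemic cytokines, and H1b expects it to raise sputum neutrophilia and IL-6. A shared cause produces a correlation between compartments even when one has no effect on the other.

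At stake is the interpretation of Aim 1. The Background (potential biological pathways) argues that systemic changes in PTSD may drive a neutrophilic airway phenotype, and links identification of these pathways to disease management and therapeutic targets. Whether airway changes follow from systemic inflammation or arise beside it bears directly on that.

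**Working it through.** **The plan's own figure.** The documents give no power or error rate for the mediation test, so there is none to reproduce. Table 3 concerns PTSD-marker comparisons only.

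**Inputs from the documents.** PTSD prevalence is about 30%. There are 175 sputum participants, and retention is at least 80%, so 175 × 0.8 = 140. Table 3 has IL-6 4 (2) with a difference of 2; reading 2 as the SD, this is 1 SD. Table 3 has neutrophilia 0.25 with a difference of 0.30, so 0.55; on the probit scale, Φ⁻¹(0.55) − Φ⁻¹(0.25) = 0.126 + 0.674 = 0.80 SD.

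**Assumptions.** Two-sided alpha is 0.05. The IL-6 effect is applied to plasma and the 0.8 SD to the airway marker, although Table 3 does not say which compartment its IL-6 row describes. Marker-to-morbidity coefficients are not in the documents and are varied.

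**Unadjusted plasma-sputum correlation with no true link.** With p = 0.3, p(1 − p) = 0.21 and PTSD effects δ₁ and δ₂ in SD units:

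r = 0.21 δ₁δ₂ / √[(1 + 0.21 δ₁²)(1 + 0.21 δ₂²)]

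P(significant) ≈ Φ(√(n − 3) · atanh r − 1.96)

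- Effects 1 and 0.8: r = 0.168 / √(1.21 × 1.134) = 0.143. This gives 39% at n = 140 and 47% at n = 175; simulations gave 36-47%.
- Effects 0.5 and 0.5: r = 0.0525 / 1.0525 = 0.050. This gives about 8% and 10%.
- Adjusted for PTSD: about 5%, the nominal level.

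**Simulation of the two steps.** The model is S = a_S·PTSD + e; A = a_A·PTSD + d·S + e; Y = b_S·S + b_A·A + 0.2·PTSD + e. S is systemic, A is airway and Y is morbidity. The link in question is d. Step 1 requires PTSD to be significant for both S and A. Step 2 is tested in a model of Y with PTSD, both markers and PTSD × marker terms. It can be read in two ways.

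| Step 2 requires | True state (a_S = 1, a_A = 0.8 unless noted) | Both steps pass (n = 140-175) |
|---|---|---|
| Airway marker only | No link, b_A = 0.1 | about 22-24% |
| Airway marker only | No link, b_A = 0.2 | 61-73% |
| Airway marker only | No link, b_A = 0.3 | 91-97% |
| Airway marker only | Link d = 0.4, b_A = 0.3 | 93-97% |
| Airway marker only | No link, b_A = 0.3, PTSD effects 0.5 SD | 55-68% |
| Both markers | No link, only airway acts on morbidity | about 5% or less |
| Both markers | No link, each acts on morbidity (0.3) | 85-95% |
| Both markers | True chain, plasma acts on morbidity only through the airway | about 3-6% |

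Repeat runs move these by a few points. On the first reading, at b_A = 0.3, the pass rate is the same with and without the link. On the second, a true chain usually fails, because plasma has no remaining association with morbidity once the airway marker is in the model, while unlinked parallel mediators usually pass if each has its own effect.

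**The serial indirect effect** a_S × d × b_A with a Monte Carlo 95% CI excludes zero in about 2-5% of studies with no link (b_A = 0.3), in 93-97% at d = 0.4, and in about 59-70% at d = 0.2.

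**The case against.** The best defense is that the SEM is under-described rather than wrong. Its stated purpose names the chain, it points to further details, and those include indirect effects and Monte Carlo CIs. The Aim 3 text also plans a model of how biological and behavioral pathways interrelate, by reference to Figure 1, which is not available here. A drawn systemic-to-airway path cannot be ruled out. This stands against any claim that the link is never tested. It does not supply the missing path in the written criteria.

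A reader might also infer that the plan would usually confirm a false chain. The documents do not support that. The high rates need marker-morbidity effects that are assumed. If step 2 must hold for both markers and only the airway marker acts on morbidity, false support is about 5% or less. The simulations also use regression rules, not the full SEM, and omit the listed confounders and the false discovery rate control.

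A third inference would be that the plan could find inflammation related to morbidity when it is not. Step 2 tests exactly whether "these factors are also associated with asthma morbidity measures while controlling for PTSD". With no marker-morbidity effect, the two steps pass in about 5% of studies on the airway-only reading, and in under 1% if both markers must predict.

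Finally, H1a to H1c are pairwise associations with their own analyses, and are unaffected. This limits the reach of the point to the mediation claim.

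**Conclusion.** The point holds as a specification gap. The stated hypothesis is serial, and the written criteria contain no PTSD-adjusted systemic-to-airway path, so they cannot separate the chain from parallel mediators. This follows from the text and needs no assumed effect size.

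The size does depend on assumptions. With no link, the unadjusted plasma-sputum association misleads in about 36-47% of studies under Table 3-sized PTSD effects, and in about 10% under 0.5 SD effects. The two-step rule's false support runs from about 5% or less to 97%, according to the marker-morbidity effects and the reading of step 2. No single figure in that range should be quoted as the plan's error rate. The marker-to-morbidity link is not at issue.

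**What to change.** In the Aim 1 SEM:

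1. Specify a path from plasma cytokine to month-1 sputum neutrophils and IL-6, adjusted for PTSD and the listed confounders. Plasma is drawn at baseline, so a time-ordered path is available.
2. Make the test of the chain the serial indirect effect (PTSD to plasma × plasma to sputum × sputum to morbidity) with a Monte Carlo 95% CI.
3. Report PTSD to sputum not via plasma as a separate path.
4. Use the PTSD-adjusted plasma-sputum association, in place of the unadjusted one, as evidence for the link.

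The cost is SAP wording and a little more analysis, with no new samples or visits. The chain becomes harder to support if the link is weak: power is about 59-70% at an assumed path of 0.2 (airway-to-morbidity coefficient 0.3).
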